After enrollment, the participants will be randomized in a 1:1 ratio having either oropharyngeal swab performed including the posterior oropharyngeal wall and both palatine tonsils (intervention group) or only including the posterior oropharyngeal wall and avoiding the palatine tonsils (control group), see Figure B.

A block randomization list was generated by [name] using an online randomization software⁽⁷⁾ afterward uploaded to REDCap. The randomization group will be disclosed in connection with trial registration in REDCap using the REDCap “randomize” function. The oropharyngeal sample will afterward be performed by the trained healthcare workers with or without the palatine tonsils depending on the randomization to either the intervention or control group.

Figure B. Study flowchart.

The swabs will be placed in separate tubes dry and sent to the clinical microbiology laboratory for detection of SARS-CoV-2 by single-target RT-PCR at Statens Serum Institute. Samples with viral cycle threshold (Ct) values below 38 are considered positive, 38-40 inconclusive and above 40 negative⁽⁸⁾.

All participants are required to fill out a survey on-site about their reason for being tested, prior Covid-19 infection(s), vaccinations status, symptoms, and if any prior tonsillectomy has been performed (appendix 2).

All healthcare workers participating in the data collection have been given a unique ID which will be registered for each OPS performed in the study. Further, the healthcare worker will also be asked to rate the Mallampati score of the participants including in the study (appendix 5).

All data will be documented on-site in a secure web database (REDCap, appendix 3).

Outcomes

The primary outcome will be reported as:

- SARS-CoV-2 RNA by RT-PCR test result (positive, negative, inconclusive)

The secondary outcome will be reported as:

- SARS-CoV-2 RT-PCR cycle threshold (Ct) value
- Test discomfort on a 11-point NRS-scale
- Development of COVID-19 disease after testing
- SARS-CoV-2 detection rate for each healthcare worker
- Mallampati Score of participants being tested

Sample size

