Based on a SARS-CoV-2 test positive proportion on 13% in the Danish capital region the last week of October 2022, we expected proportion of positive to increase to about 20% during the following study period⁽⁹⁾. The power calculation was based on an expected improvement in diagnostic accuracy of 25% by including the palatine tonsils in the oropharyngeal specimen collection compared to a sample without the tonsils. We therefore estimated that a sample of 2,188 participants (with about 438 with SARS-CoV-2 infection) would provide the trial with 80% power at a 5% significance level with an expected test positive proportion of 20% for SARS-CoV-2

among the participants tested ⁽¹⁰⁾. As we expect about 10% missing due to dropout and missing data, we aim to include 2,407 participants in the study. All individuals entering the testing facility who meet the eligibility criteria are offered to participate in the study. We expect about 300-700 tests performed at both COVID-19 test centers each day and an assumed participation at 10-30%. We therefore expect to complete the study within two-three months.

Statistical analysis

A study participant is considered to have a SARS-CoV-2 infection if the oropharyngeal sample is RT-PCR positive (reference standard). Participants with an inconclusive RT-PCR test result will be included in the analyses as a negative test result following an intention-to-diagnose approach⁽¹¹⁾. Differences in the proportion of SARS-CoV-2 positive tests between the intervention and the control group will be compared using binary logistic regression using test center as fixed effect and a generalized estimating equation to adjust for clustering of data within the healthcare workers performing the sample. The difference in SARS-CoV-2 detection rate between healthcare workers will also be reported separately to estimate the inter-person variance. The Ct values from positive RT-PCR samples and the NRS discomfort scores will be compared using a general linear model with mixed effects (Ct) and GEE models (NRS discomfort). The 95% confidence intervals (CI) will be presented. Categorical data will be summarized with number and percentage while continuous data will be summarized by mean and standard deviation. We will not perform tests of statistical significance for baseline characteristics. 5% significance level was applied. Statistical Analysis Software ver. 9.4 (SAS Institute, North Carolina, U.S.) was used for the statistical analyses.

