3.3 Missing data

Participants who will not adhere to the intervention definition (see SAP 1.2) will be reported as missing data and excluded from final analysis. Participants with missing data about their baseline characteristics from the questionnaire will still be included in the statistical analysis of primary outcome and secondary outcome. A table with baseline characteristics will be presented as raw data without the participants with missing data from the questionnaire.

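### The recruitment target of 2,407 adds 10% to the required 2,188 instead of dividing by 0.90, so it covers a 9.1% loss from the primary analysis; the effect is minor

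*Combined protocol and SAP*

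**What the plan says.** The Sample size section of the protocol gives the required number: "We therefore estimated that a sample of 2,188 participants (with about 438 with SARS-CoV-2 infection"), which "would provide the trial with 80% power at a 5% significance level". The recruitment target follows: "As we expect about 10% missing due to dropout and missing data, we aim to include 2,407 participants in the study". Its only stated purpose is to absorb that loss.

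The SAP settles which losses reduce the analysed number:

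- **SAP 1.2** removes participants with no CPR number, test center, randomization group or RT-PCR result on record.
- **SAP 3.3** says that those who do not meet the adherence definition in 1.2 "will be reported as missing data and excluded from final analysis". Its next sentence keeps participants who lack only baseline questionnaire data in the primary and secondary analyses.
- **SAP 2.4** expects no dropout after the single swab, apart from missing data.

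**The concern.** When a fraction d of recruits will be lost from the analysis, the number to recruit is the required number divided by (1 − d). Multiplying by (1 + d) gives too few, because the loss falls on the larger recruited number. The plan appears to have multiplied. If so, its target does not quite cover a loss of exactly 10%, and the trial would end slightly below the size it set itself. At stake are the accuracy of a stated design figure and a small amount of power.

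**Working it through.** **Inputs**

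- Required analysable number: 2,188, or 1,094 per arm (protocol, Sample size).
- Loss: about 10% (protocol, Sample size).
- Recruitment target: 2,407 (protocol, Sample size).
- Power 80%, significance level 5% (protocol, Sample size). Sidedness is not stated.
- Allocation: "the participants will be randomized in a 1:1 ratio" (protocol, randomization section).
- Positive rate: "with an expected test positive proportion of 20% for SARS-CoV-2" (protocol, Sample size). I take it as the control rate, which is an assumption.
- Effect: "The power calculation was based on an expected improvement in diagnostic accuracy of 25" per cent (protocol, Sample size). I read it as relative, 20% to 25%, which is also an assumption.

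**1. Reproduce the required number.** For two proportions with a pooled test and no continuity correction,

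n per arm = [1.960 × √(2 × p̄(1 − p̄)) + 0.8416 × √(p₁(1 − p₁) + p₂(1 − p₂))]² / (p₂ − p₁)²

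With p₁ = 0.20, p₂ = 0.25 and p̄ = 0.225, the two roots are 0.5906 and 0.5895, and n = 1,093.7. Rounded up, this is 1,094 per arm, or 2,188 in total: an exact match. With the same rates, a continuity correction gives 2,268 and a one-sided test gives 1,724. The 20% v 25%, two-sided reading is thus well supported, but it is inferred.

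**2. Reproduce the target.** 2,188 × 1.10 = 2,406.8, rounded up to 2,407: an exact match.

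**3. Target that matches a 10% loss.** 2,188 / 0.90 = 2,431.1, rounded up to 2,432. This is 25 more than 2,407 (25 / 2,407 = 1.0%).

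**4. Loss that 2,407 can absorb.** 1 − 2,188 / 2,407 = 0.091, or 9.1%.

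**5. Analysable number from 2,407, by loss**

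| Loss from primary analysis | Remaining | Against 2,188 |
|---|---|---|
| 8% | 2,214 | +26 |
| 9% | 2,190 | +2 |
| 9.5% | 2,178 | −10 |
| 10% | 2,166 | −22 |
| 11% | 2,142 | −46 |

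**6. Power under the inferred inputs.** At 2,188 it is 80.0%; at 2,166 it is 79.6%. The difference is about 0.4 points. These figures ignore the clustering by healthcare worker for which the primary analysis adjusts.

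**7. Does the power cost depend on the inferred rates?** Suppose instead that 20% is the overall positive rate and the relative gain is 25%. Then p₁ = 0.40 / 2.25 = 17.8% and p₂ = 22.2%. Power is 73.9% at 2,188 and about 73.5% at 2,166. The absolute level changes, but the loss is still about 0.4 points. The shortfall of 22 depends on none of these rates.

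**The case against.** There are four fair points on the other side.

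- **The loss is approximate.** The plan writes "As we expect about 10% missing due to dropout and missing data", and 9.1% lies within the looseness of that figure. A reader might infer that the required size, the loss rate and the target cannot all hold together. The documents do not support that: at 9% loss 2,190 remain, which is enough. What stands is that 2,407 matches exactly 10% applied by multiplication, and at that value the target falls short.
- **Not all missing data removes a participant.** SAP 3.3 keeps those who lack only questionnaire data, and the Sample size section does not say which missing data it means. If about one percentage point of the 10% were questionnaire gaps, 2,407 would suffice. SAP 2.4 also suggests that losses may be low. Even so, an allowance added to the sample size for the primary outcome is most naturally read as loss from the primary analysis.
- **The power figures are inferred.** The plan states neither 20% v 25% nor a two-sided test. Its figure of about 438 infected is 20% of all 2,188, whereas 20% and 25% in two arms of 1,094 would give about 492 positives (1,094 × 0.45). So 79.6% should not enter the protocol as a settled value. The shortfall of 22 is unaffected.
- **It is very small.** The 20% positive rate is itself a forecast, up from an observed 13%, and that uncertainty far outweighs a 1.0% gap in numbers. This bears on the weight of the point. The arithmetic is unaffected.

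**Conclusion.** The point holds as a minor arithmetic correction. The 10% was added to 2,188 when it should have been divided out, so 2,407 covers a 9.1% loss from the primary analysis. At a full 10% loss the trial analyses 2,166 participants, about 22 (1.0%) fewer than it requires, at a cost of about 0.4 points of power.

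The shortfall rests on two things: that the 10% means exclusions under SAP 1.2, and that it is taken at face value. The absolute power figures of 80.0% and 79.6% rest further on 20% v 25%, two-sided 5%, 1:1 allocation and no clustering.

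A reader might go on to infer that this slip leaves the trial materially underpowered. The figures do not show that. No analysis or conclusion changes, and a loss of 9% or less removes the shortfall altogether.

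**What to change.** Replace the sentence on the target in the Sample size section with wording such as: *A target of 2,407 allows for about 9% of participants being excluded from the primary analysis; at 10% exclusion, 2,166 are analysable.* Refer to SAP 1.2 for what counts as an exclusion, so that questionnaire gaps are not mistaken for losses. If a power figure is added, state the assumed rates and sidedness beside it.

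For reference, the target that matches a 10% allowance is 2,432, or 25 more participants.

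The cost is one sentence. Restating the allowance adds no participants and changes no procedure.

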Severe Acute Respiratory Syndrome Coronavirus 2 (SARS-CoV-2) testing strategy is essential for the diagnostic work up and screening during the coronavirus disease 19 (COVID-19) pandemic. Proper upper respiratory specimen collection is the most critical step in the diagnosis of SARS-CoV-2 virus in public settings and standard sample guidelines are recommended⁽¹⁾. An oropharyngeal swab (OPS) specimen is the preferred sample in many countries, either alone or combined with nasal swab^(2, 3). However, there is a great variability in the diagnostic accuracy for OPS with a 95% confidence interval from 52-100% reported in systematic reviews^(4, 5) and The Infectious Diseases Society of America therefore do not recommend OPS for SARS-CoV-2 testing⁽⁶⁾. Many of the previous studies performing OPS also lack detailed description of the sample technique, which makes it difficult to compare the different diagnostic accuracy results. Currently, there are no standardized oropharyngeal sample guidelines, and some only collect specimen from the posterior oropharyngeal wall while other recommend also to include a swab of the palatine tonsils for SARS-CoV-2 testing (Figure A). The Danish Health Authority advised to avoid the palatine tonsils in the oropharyngeal swab in the beginning of the COVID-19 pandemic, but later changed their recommendation so it was up to the individual testing center to decide⁽⁷⁾. However, studies suggest that the palatine tonsils could have a tissue tropism for SARS-CoV-2 which may improve the SARS-CoV-2 detection during sampling⁽⁸⁾. This may explain the variation of sensitivity reported, but no clinical studies have explored the differences between the two sample techniques. We therefore plan to conduct a randomized clinical trial to compare an oropharyngeal swab with or without the palatine tonsils.

[figure not shown]

FIGURE A. Image A. Anatomic visualization of the posterior oropharyngeal wall (green) and palatine tonsils (pink). Image B. Oropharyngeal swab including the posterior oropharyngeal wall and palatine tonsils. Image C. Oropharyngeal swab including the posterior oropharyngeal wall, but avoiding the palatine tonsils.

Research question

In a cohort of individuals tested for COVID-19 at a public test center, what is the sensitivity of an OPS sample, including the palatine tonsils, compared to only swabbing the posterior oropharyngeal wall in molecular detection of SARS-CoV-2?

Methods

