Appendix 2: Survey for participants

Survey to be filled out by participant

1. Are you vaccinated against COVID-19?

YES

NO

2. Have you previously been infected with COVID-19?

YES

NO

3. Please indicate your reason for getting tested today:

Symptoms

Close contact

Positive quick test

Screening

Test ahead of social gathering or nursing home visit

Other

If 'yes' to symptoms, which symptoms do you have?

Sore throat

Headache

Cough

Muscle and joint pain

Fever

Fatigue

Reduced sense of smell or taste

If "yes" to symptoms, for how many days have you had symptoms?

Indicate number of days: _____ day(s)

4. Have you had your tonsils removed??

YES

NO

5. On a scale from 0-10, how uncomfortable was today's test for COVID-19?

No discomfort

Worst possible discomfort

To be filled out by personnel:

REDCap ID: _____

Personnel ID: _____

Participant's Mallampati score:

1

2

3

4

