2.4 Withdrawal/Follow-up

The level of withdrawal and the missing final RT-PCR test results during the study will be tabulated. As they only had a single OPS performed, no dropouts will be expected after the intervention – beside missing data.

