3.1 Outcome definitions

The primary outcome:

- The proportion of positive SARS-CoV-2 RNA samples by RT-PCR for intervention and control group

The secondary outcome:

- SARS-CoV-2 RT-PCR cycle threshold (Ct) value
- Test discomfort on a 11-point NRS-scale
- Development of COVID-19 disease after testing
- SARS-CoV-2 detection rate for each healthcare worker
- Mallampati Score of participants being tested

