3.1 Analysis methods

Analysis method and treatment effects

Differences in the proportion of SARS-CoV-2 positive tests between the intervention and the control group will be compared using binary logistic regression using test center as fixed effect and a generalized estimating equation to adjust for clustering of data within the healthcare workers performing the sample. The difference in SARS-CoV-2 detection rate between healthcare workers will also be reported separately to estimate the inter-person variance. The Ct values from positive RT-PCR samples and the NRS discomfort scores will be compared using a general linear model with mixed effects (Ct) and GEE models (NRS discomfort).

The 95% confidence intervals (CI) will be presented. The level of statistical significance will be defined as $p < 0.05$.

Adjustment for covariates

The regression analyses will be adjusted for the effect of the test centers and the individual health-care worker performing the sample.

Methods used for assumptions to be checked for statistical methods

Assumptions for the logistic regression analysis included a binary outcome, independent observations and linearity in logit for continuous variables. To account for lack of independent observations, a generalized estimating equation approach will be applied. No continuous variables will be included.

Assumptions for the linear regression analysis included a normal distribution, independent observations, equal variation (homoscedasticity) and linearity in logit for continuous variables. Normally distributed outcomes and homoscedasticity will be evaluated visually by plots of the residuals. To account for lack of independent observations, a generalized estimating equation approach and mixed effect models will be applied. No continuous variables will be included.

Details of alternative methods to be used if distributional assumptions do not hold, e.g., normality, proportional hazards, etc.

If the assumption of a normal distribution of the outcome in the linear regression model is not fulfilled, a transformation of the outcome will be applied (e.g., logarithmic and rank transformations).

Planned subgroup analyses

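### The trial asks about relative sensitivity, but the swab is its own reference standard and no effect measure is named; the ratio of positive proportions should be the primary effect

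*Combined protocol and SAP*

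**What the plan says.** The protocol's Research question asks "what is the sensitivity of an OPS sample, including the palatine tonsils, compared to only swabbing the posterior oropharyngeal wall". Under Statistical analysis the protocol states: "A study participant is considered to have a SARS-CoV-2 infection if the oropharyngeal sample is RT-PCR positive (reference standard". SAP 2.4 confirms that there is one swab per person: "As they only had a single OPS performed, no dropouts will be expected after the intervention". Under Follow-up, only participants with a positive result are contacted afterwards.

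SAP 3.1 (Outcome definitions) gives the primary outcome as "The proportion of positive SARS-CoV-2 RNA samples by RT-PCR for intervention and control group". SAP 3.1 (Analysis methods), like the protocol, says the arms will be "compared using binary logistic regression using test center as fixed effect", with a GEE for clustering by healthcare worker. Neither document says whether an odds ratio, a ratio or a difference of proportions will be reported.

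The Sample size section rests on "an expected improvement in diagnostic accuracy of 25% by including the palatine tonsils". The opening of Methods and the Ethics section describe the aim as comparing detection rates. A Bayesian latent class analysis of sensitivity and specificity appears under Planned subgroup analyses, without model structure or priors.

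**The concern.** Three parts of the plan point at different quantities. The question asks for sensitivity. The case definition makes sensitivity 100% by construction. The model, left to its default, yields an odds ratio. The design can deliver something useful that none of these names: because randomisation balances infection prevalence between arms, the ratio of positive proportions estimates relative sensitivity when specificity is near perfect.

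What is at stake is the meaning of the headline number. A gain of 25% in detection would appear as an odds ratio of 1.33, which is easily read as a gain of 33%. The quantity on which the trial was sized would have no prespecified adjusted estimate or interval.

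**Working it through.** **Inputs.** From Sample size: 20% expected positive, 25% improvement, 80% power, 5% significance, 2,188 participants, and 13% positive at the time of planning. From the randomisation section: 1:1 allocation.

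**1. Reproduce the sample size.** Take p0 = 0.20, p1 = 1.25 × 0.20 = 0.25, two-sided 5%, pooled variance under the null:

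n = [1.960·√(2 × 0.225 × 0.775) + 0.842·√(0.20 × 0.80 + 0.25 × 0.75)]² / 0.05² = 1,094 per arm, or 2,188 in total.

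This matches exactly. The planned 25% is therefore a ratio of positive proportions, 1.25.

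**2. Apply the reference-standard rule literally.** If infected means swab-positive, sensitivity = P(positive | positive) = 100% in each arm. At the design alternative the rule also makes infection differ between randomised arms: 1,094 × 0.20 ≈ 219 v 1,094 × 0.25 ≈ 274.

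**3. What the arms can estimate.** With true prevalence π (equal by randomisation), the positive proportion in an arm is Se·π + (1 − Sp)(1 − π). If Sp = 1 in both arms, p1/p0 = Se1/Se0 and π cancels.

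**4. What the logistic model gives.** OR = [p1/(1 − p1)] / [p0/(1 − p0)], with p1/p0 held at 1.25:

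| Control positive | Tonsil arm | Ratio | Difference | Odds ratio |
|---|---|---|---|---|
| 13% | 16.25% | 1.25 | 3.25 points | 1.30 |
| 20% | 25% | 1.25 | 5 points | 1.33 |

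In reverse, an odds ratio of 1.33 corresponds to a ratio of 1.28 at 13% and 1.25 at 20%.

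**5. Precision at the design point, ignoring clustering.** SE(log ratio) = √(0.80/218.8 + 0.75/273.5) = 0.080, giving a 95% CI of about 1.07 to 1.46. SE(log OR) = √(1/218.8 + 1/875.2 + 1/273.5 + 1/820.5) = 0.103, giving about 1.09 to 1.63.

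**6. Imperfect specificity.** Assumed, not in the documents: sensitivities 0.64 v 0.80 (true ratio 1.25) and specificity 98% in both arms. At 13% prevalence:

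- control: 0.64 × 0.13 + 0.02 × 0.87 = 0.1006
- tonsil arm: 0.80 × 0.13 + 0.02 × 0.87 = 0.1214
- ratio: 1.21

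At 99% specificity the ratio is 1.23.

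**7. Latent class analysis.** One test per person in two arms gives two free proportions. The unknowns are prevalence, two sensitivities and two specificities: five, or four with a common specificity. Even with specificity fixed at 1, three unknowns face two proportions. Any separate estimate of each sensitivity would come from the priors.

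**The case against.** The best defence is that the primary analysis never computes sensitivity against the circular standard. It compares positive proportions between randomised arms, which is the detection-rate aim stated in Methods and Ethics. On that reading the sentence is only a case definition and the fault is one of wording. This stands in part: the circularity changes no number in the primary comparison. It does not remove the conflict with the Research question, and an aim framed as detection rate also calls for a ratio or difference of proportions.

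Second, no passage names an odds ratio. That is correct; it is inferred from the choice of logistic regression. Percentages per arm will presumably be reported, so a crude ratio could be recovered, but not one adjusted for centre and clustering with a prespecified interval.

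Third, the proposed ratio is not free of prevalence either. With the assumed sensitivities and 98% specificity it is 1.21 at 13% prevalence and 1.16 at an assumed 5%. This is true and is why the specificity assumption must be stated.

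A reader might go further in three ways that the documents do not support:

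- **That the estimate swings widely with prevalence.** Over the only range given, 13% to 20%, the odds ratio moves from 1.30 to 1.33, which is small beside an interval of about 1.09 to 1.63. Larger gaps need control positivity well above anything documented.
- **That subgroups with more infection will show spuriously larger odds ratios.** The plan promises only to explore the distribution of positive results by stratum; it specifies no stratum-specific odds ratios or interaction tests.
- **That attenders who tick "Positive quick test" in Appendix 2 supply an independent reference standard.** This is a self-reported reason for attending, with no test type, date or confirmation recorded, and the size of the group is not given. A comparison within it could be exploratory at most.

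**Conclusion.** The concern holds as a mismatch between question, case definition and effect measure. Under the stated rule sensitivity cannot differ between arms. The trial is sized on a ratio of 1.25, while the only specified model naturally gives 1.33 at that point.

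It would be wrong to infer that the primary test is invalid. If specificity is equal in the two arms, the odds ratio is 1 exactly when the sensitivities are equal, so the null hypothesis is unaffected. The sample size is also unaffected, because it was computed on proportions.

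Reading the ratio as relative sensitivity rests on equal, near-perfect specificity, with shortfalls pulling it towards 1. The latent class analysis cannot stand in for it without informative priors, and none are given. The change is worth making before analysis because it lets the trial answer its own question at almost no cost.

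**What to change.** 1. In the protocol's Statistical analysis and SAP 3.1 (Analysis methods), name the ratio and the difference of positive proportions, each with a 95% CI, as the primary effect. Obtain them by marginal standardisation from the GEE already planned, or with a log link. The odds ratio may be reported as well.
2. State that the ratio estimates relative sensitivity only if specificity is equal and near perfect in both arms, and that lower specificity pulls it towards 1. The illustration above (1.21 instead of 1.25) can be given, with its assumptions.
3. Limit the reference-standard sentence to a definition of detected infection.
4. Align the Research question with the detection-rate aim in Methods and Ethics, or word it as relative sensitivity under the stated assumption.

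The cost is SAP wording and a few lines of SAS. No new data are needed and N stays at 2,188 evaluable. The downside is that the headline ratio will look slightly smaller than the odds ratio. The Data plan rules out analysis before data collection is completed, so the change belongs before that point.
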